Visit 1 will be performed on the 28th day after birth and the intervention period will last 332 days (slightly changed by clinic visit time) consisting of 3 visits: Visit 2 (90 ± 3 days after birth), Visit 3 (180 ± 5 days after birth), and Visit 4 (360 ± 7 days after birth). Subjects in each group will be enrolled 1:1 and based on an expected completion rate of 80%, 64 subjects are expected to complete the trial. Participants who withdrew from the study before Visit 4, failed in three contacts, met the withdrawal criteria, seriously violated the trial protocol, or met other withdrawal criteria were excluded by the investigators.

In addition, indicators and incidence of adverse events (e. g. eczema) will be recorded and compared during the study. For the purposes of this trial, adverse events were defined as any adverse and unexpected signs (including other abnormal laboratory results beyond the study plan), symptoms, disease related to participation in the clinical trial, and the disease related to the trial product.

5 subject investigated

Infants born 0 to 28 days after birth are screened and who meet all inclusion criteria and do not meet any exclusion criteria will be assigned to the breastfeeding group or randomized to the trial / control group.

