5.3 Exit standard

• Ineligible (ignored during screening, occurred during the study or found by review);

- Serious protocol deviation occurs;
- Serious non to protocol or test requirements;

[figure not shown]
• Need to terminate the designated formula due to adverse events or cause failure to continue following the trial procedures;

• Need to discontinue the designated formula or cause the inability to follow the trial procedures due to disease progression;

- Withdraw informed consent or remove informed consent;
- Misvisit.

6 research design

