6.7 Subjects stopped / withdrew from the trial

The guardian of the subject has the right to withdraw the infant from the trial at any time. In addition, the investigator may discontinue the subject at any time if the investigator considers it necessary for reasons including:

• Ineligible (ignored during screening, occurred during the study or found by review);

- Serious protocol deviation occurs;
- Serious non to protocol or test requirements;
- Termination of the designated formula or failure to follow the trial procedures due to an adverse event;

• Need to discontinue the designated formula or cause the inability to follow the trial procedures due to disease progression;

- Withdraw informed consent or remove informed consent;
- Misvisit.

If a subject withdraws from the trial due to an adverse event, the investigator will schedule a follow-up visit or telephone visit until the adverse event is resolved or is stable. Data collected before withdrawal will be used for analysis. If a subject withdraws from the trial, the subject will not be replaced. The reason for the withdrawal will be documented in the case report form.

7 Research products

7.1 burden

(1) Ingredients list of test milk powder

The test milk powder was produced by Feihe (Jilin) Dairy Co., LTD. Three formulations were used for infants aged 0-3 months, 3-6 months and 6-12 months respectively. All products are produced in strict accordance with Good Production Practice (GMP), and all indicators meet the requirements of relevant standards and regulations. Compared with the control milk powder, 2 ' -fucinose based lactose, lactose-N-new tetrosaccharide, bifidobacterium longum BB536 are the added ingredients unique to the test milk powder, and the ingredients are as follows:

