9.3 Analyze the crowd

The Statistical analysis population data sets were defined as follows:

Screening Set (Screening Set): includes all subjects who signed the informed consent and participated in trial screening.

Full Analysis Set (Full Analysis Set, FAS): All subjects who participated in the trial and completed at least Visit 1. The FAS set is the main population for the efficacy analysis.

Compliance Set (Per-Protocol set, PPS): is a subset of the full analysis set containing subjects who completed all visits to the trial and had no major protocol deviations during the trial. The PPS set is a secondary population for the efficacy analysis.

Safety Analysis Set (Safety Set, SS): The Safety Analysis Set includes all subjects who participated and received test samples with records of safety indicators.

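### Section 4 excludes serious protocol violators without condition, which conflicts with 6.7 or 9.3 on either main reading and can cost the primary comparison its later stool samples

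*Protocol*

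**What the plan says.** Four places in the Protocol bear on what happens to an infant with a serious deviation.

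- **Section 4 (research contents).** After giving the expected number of completers, it lists infants who withdrew before Visit 4, could not be reached after three attempts, met withdrawal criteria, or "seriously violated the trial protocol, or met other withdrawal criteria were excluded by the investigators". No discretion is mentioned.
- **Section 5.3 (Exit standard).** A list of seven reasons with no operative verb. It includes "Serious protocol deviation occurs" and "Serious non to protocol or test requirements".
- **Section 6.7.** The same seven reasons, introduced by "the investigator may discontinue the subject at any time if the investigator considers it necessary for reasons including". It adds "Data collected before withdrawal will be used for analysis". The only contact planned after exit is for adverse events: "If a subject withdraws from the trial due to an adverse event, the investigator will schedule a follow-up visit or telephone visit". Withdrawn infants are not replaced.
- **Section 9.3.** The FAS is everyone who took part and completed at least Visit 1, and it is the main efficacy population. The per-protocol set (PPS), a secondary population, contains "subjects who completed all visits to the trial and had no major protocol deviations during the trial".

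Stool for 16S rRNA and SCFAs, the primary endpoint in 8.1, is listed at Visits 1, 3 and 4 only (6.6.1, 6.6.3, 6.6.4). Section 9.2 rules out imputation.

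**The concern.** Section 4 gives an unconditional rule for a class of infants that 6.7 treats as a matter of judgement and that 9.3 keeps in the main population. A centre that follows section 4 and a centre that follows 6.7 could treat the same infant differently.

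This affects the primary comparison, the change in flora between test and control formula (9.7.1). Whether a randomised infant with a deviation has stool at days 180 and 360 could depend on which passage is read, or on a judgement made after randomisation. A later statistical analysis plan can define populations, but it cannot recover stool that was never collected. That makes this a matter for the protocol.

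**Working it through.** **1. The plan's own figure.** From section 4 and 6.5.2: 80 per group and 20% loss. 80 × (1 − 0.20) = 64, and 64 / 0.80 = 80. The stated 64 is reproduced. Expected exits are 80 − 64 = 16 per group, or 32 of the 160 randomised.

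**2. What excluded can mean in section 4.**

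| Reading | Against 6.7 | Against 9.3 |
|---|---|---|
| Discontinued from the trial | Conflicts: 6.7 is discretionary | No direct conflict; the infant stays in the FAS with early data only |
| Left out of the analysis | Conflicts: 6.7 uses data gathered before withdrawal | Conflicts: the FAS has no exclusion for deviations |
| Not counted among the 64 completers | No conflict | No conflict |

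The first two readings have a practical effect, and each contradicts another section. The third is taken up under the objection. The Protocol also uses serious (4, 5.3, 6.7) and major (9.3) for deviations without linking or defining them.

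**3. Consequence for the stool data.** An infant who exits after Visit 1 and before Visit 3 has a Visit 1 sample only. One who exits between Visits 3 and 4 has no day-360 sample. With no later sampling planned and no imputation, the FAS at day 360 consists in practice of those who reach Visit 4, about 64 per group. These are nearly the same infants who can qualify for the PPS, so the secondary set gives little check on the main one at that visit.

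**4. Upper bound on the numbers.** The share f of exits due to deviation or non-compliance is not stated, so it is varied as an assumption. Also assumed: all 80 give Visit 1 stool, and loss is even over days 28 to 360 (332 days).

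- Lost by day 180: 16 × 152/332 = 7.3, leaving 72.7 per arm.
- Stool planned per arm: 80 × 3 = 240. Expected: 80 + 72.7 + 64 = 216.7.
- Infants keeping day-360 stool if all such exits still gave samples: 16 × f. At day 180: 7.3 × f.

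| f | Extra at day 180 | Extra at day 360 | n at day 360 | Extra samples per arm |
|---|---|---|---|---|
| 0.25 | 1.8 | 4 | 68 | 5.8 |
| 0.5 | 3.7 | 8 | 72 | 11.7 |
| 1 | 7.3 | 16 | 80 | 23.3 |

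The row f = 1 is a ceiling only. It would mean that nobody leaves for adverse events, disease, withdrawn consent or missed visits.

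**5. Precision.** Detectable standardised difference, assuming 80% power and a two-sided 5% t-test (the Protocol states no power or effect size): 0.499 at 64 per arm, 0.484 at 68, 0.470 at 72, 0.446 at 80. By the normal approximation, (1.960 + 0.842) × √(2/n) gives 0.495 at 64 and 0.443 at 80.

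**6. Selection, as illustration only.** If arms lose shares e1 and e0, and leavers differ from stayers by g SD in both arms, the contrast among stayers shifts by (e1 − e0) × g. With assumed exits of 25% against 15% and g = 0.25, the shift is 0.025 SD. With 30% against 10% and g = 0.5, it is 0.10 SD. With equal exit rates it is 0. These figures cover exits of every kind, so compliance exits would account for only part of any shift.

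**The case against.** The strongest reply is that section 4 only says who is not counted as a completer. The sentence directly follows the expected 64, and its list begins with infants who have already withdrawn or been lost, whom nobody can discontinue. On that reading nothing conflicts. The reading is possible, but it is the weaker one: the text describes an action by the investigators and does not mention the completer count. The possibility does mean that section 4 cannot be reported as plainly ordering discontinuation.

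A reader might also infer that the Protocol sets three rival rules. It does not. Section 5.3 is a bare list, and 6.7 repeats that list and supplies the verb. Sections 6.7 and 9.3 are compatible: an infant discontinued after Visit 1 stays in the FAS with the data collected so far and is outside the PPS. The outlier is section 4.

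Three further replies stand. The lack of stool after exit follows from the visit schedule and the limited follow-up in 6.7, not from a stated prohibition. The table by f sizes what continued sampling could yield. The gap between section 4 and 6.7 is smaller, because it concerns only infants an investigator would choose to keep. And "Ineligible (ignored during screening, occurred during the study or found by review" can describe a clinical event, so that reason cannot be treated as a pure compliance matter.

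**Conclusion.** Section 4 is inconsistent with 6.7 if it means discontinuation, and with both 9.3 and 6.7 if it means exclusion from analysis. If it is followed, randomised infants are lost from the day-180 and day-360 flora comparison because of a compliance judgement made after randomisation, and the FAS at day 360 comes close to the completers, about 64 of 80 per group.

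A reader might infer that the formula comparison is biased. The documents do not support that. They give neither the share of exits due to deviation nor any difference between arms, so selection bias can be neither shown nor sized. The effect on precision is small, at most 0.50 against 0.45 SD under the assumed power and test. Some closeness of FAS and PPS at day 360 would arise from ordinary loss without imputation in any case.

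The trial is exploratory and treats inference as for reference only (section 4 and 9.2), so the point concerns which infants the group summaries describe. Severity is minor to moderate.

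**What to change.** 1. Reconcile section 4 with 5.3, 6.7 and 9.3. For example, replace the statement that these infants were excluded with a cross-reference: they are handled under 6.7, are not in the PPS, and, if they completed Visit 1, stay in the FAS with all data collected. Say whether serious and major deviations are the same thing.
2. State in 6.7 that a protocol deviation or non-compliance does not by itself end data collection. The stool already scheduled at Visits 3 and 4 is still collected where the guardian agrees and contact is kept.

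Whether and when an infant stops the formula or leaves for clinical reasons, including ineligibility that arises during the study, is not judged here. The sponsor must reconcile those passages.

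The cost is wording in sections 4, 5.3 and 6.7, and a few more stool samples than expected under 20% loss: about 6 to 12 per formula arm if a quarter to a half of exits are of this kind, and never more than about 23. All fall within the 240 samples per arm already planned. No infants, visits or assays are added, and 6.5.2, 9.2 and the set definitions in 9.3 can stay.

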9.5 Demographic data

Subject demographic data will be summarized according to the full analysis set. The summary of demographic data should include the following: (1) age (age year) - the difference between the date of signed informed consent and the date of birth / 365.25; (2) gender- -male / female; (3) ethnic group- -Han / other.

9.6 adverse event

All reported adverse event names and terminologies need to be coded in the latest version of the MedDRA. For all adverse event tables, subjects were counted only once in each preferred term (Preferred Term, PT) and systemic organoids (System Organ Class, SOC). Unless specifically defined, adverse events were ranked in descending order of the preferred term frequency in each system organ class. If several preferred terms in the same system organclass have the same frequency, then in the literal order of preferred terms.

All adverse events will be summarized by SOC, PT and CTCAE criteria, including

• Number of subjects, percentage of adverse events, and number of adverse events

• Number and percentage of subjects with serious adverse events and number of adverse events

• Number of subjects with early withdrawal due to adverse events and number of adverse events

All adverse events will be displayed as lists.

9.7 efficiency analysis

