10.2 Management of the adverse events

An adverse event is an adverse event after a patient or a clinical study subject receives an investigational product that does not necessarily be causally related to the trial. Adverse events are laboratory findings of disease, signs or symptoms, and / or abnormalities during the course of the study. Adverse events include subjects in contacting the investigator or their personal physician, being examined or given medical guidance. This may or may not cause the subject's withdrawal from the study. Adverse events are generally classified as serious or not serious.

All adverse events during the study should be reported and recorded, regardless of whether they are considered serious or not serious and treatment-related. Each case should include the following: subject and date, description of the event, duration, frequency, degree, severity, actions taken, results and sequelae, and relationship to the tested product.

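### Section 4 defines adverse events more narrowly than 10.2, and 10.1 relies on a lactose-intolerance exclusion that neither 5.2 nor the synopsis lists

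*Protocol*

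**What the plan says.** **Adverse events.** Section 4 gives a definition that it presents as specific to the study: "adverse events were defined as any adverse and unexpected signs (including other abnormal laboratory results beyond the study plan), symptoms, disease related to participation". The sentence then adds disease linked to the product. The sentence just before it says that "incidence of adverse events (e. g. eczema) will be recorded and compared during the study".

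Section 10.2 describes an adverse event as one occurring "after a patient or a clinical study subject receives an investigational product that does not necessarily be causally related to the trial". It continues: "Adverse events are laboratory findings of disease, signs or symptoms, and / or abnormalities during the course of the study". It then gives the recording rule, "All adverse events during the study should be reported and recorded, regardless of whether they are considered serious or not serious and treatment-related", and lists what each record must hold, ending with "actions taken, results and sequelae, and relationship to the tested product".

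Section 8.3 names adverse events and serious adverse events as the only safety index. Section 9.6 summarises them by system organ class, preferred term and CTCAE criteria, and adds that "All adverse events will be displayed as lists".

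**Lactose intolerance.** Section 10.1 notes that both powders contain lactose and milk protein. It foresees two reactions, lactose intolerance and milk protein allergy, and says that lactose-intolerant infants were excluded at screening. Section 5.2 and the synopsis carry the same nine exclusion criteria. One concerns IgE-mediated milk protein allergy or a raised risk of it. None names lactose intolerance.

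**The concern.** What counts as an adverse event is applied by site staff when they decide whether to enter one. Section 9.6 can tabulate only what was entered, and no later analysis can recover an event that was not. If relatedness is part of the definition, the site's causal judgement comes before recording and shapes the numerator. If it is a field completed afterwards, every event is there to be counted. The protocol contains both rules, and in a multicenter trial different sites may follow different ones.

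On lactose, 10.1 presents screening as a safeguard against a reaction it foresees. Sections 5 and 6.4 enrol on the listed inclusion and exclusion criteria. Staff who screen from those lists are not told to apply the safeguard. It is also unclear whether an infant later found to be lactose-intolerant counts as ineligible under the first exit reason in 5.3, because that depends on which passage is taken as the eligibility rule.

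**Working it through.** There is no figure in the plan to reproduce. The check is a comparison of passages.

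**1. Adverse event definition.** The grammar of the Section 4 sentence is loose, so two readings are tested. On the narrow reading, *unexpected* qualifies only signs and *related* qualifies only disease. On the wide reading, both qualify signs, symptoms and disease.

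| Event | Section 4, narrow | Section 4, wide | 10.2 |
|---|---|---|---|
| Disease judged unrelated | outside | outside | recorded |
| Sign regarded as expected | outside | outside | recorded |
| Symptom judged unrelated | inside | outside | recorded |
| Unexpected sign judged unrelated | inside | outside | recorded |

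The first row is the firm result: on either reading, unrelated disease falls outside Section 4 and inside 10.2. The second row also survives both readings, but it hangs on one word in a rough translation, and the protocol gives no list of expected events against which a site would apply it. It is the weaker half. The last two rows depend on the parsing and are not relied on.

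Section 10.2 also shows the order of steps it intends. It asks for the relationship to the product in each record, which makes sense only if unrelated events are entered first. No passage ranks Section 4 and 10.2.

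**2. Lactose-intolerance exclusion.** The nine criteria in 5.2 were checked one by one:

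- assisted reproduction;
- maternal disease that may harm intrauterine growth;
- gestational diabetes, or severe metabolic or chronic maternal disease;
- congenital malformation, or genetic, chronic or congenital disease that may interfere with the study;
- milk protein allergy or raised risk of it;
- acute infection or gastroenteritis;
- functional gastrointestinal disease, with gastroparesis as the example;
- participation in another trial;
- doubt about the parents' willingness or ability to comply.

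Milk protein allergy is named in 1 of 9 and lactose intolerance in 0 of 9. The synopsis gives the same counts. The allergy item cannot stand in for lactose intolerance, because 10.1 treats the two as separate reactions. The congenital, genetic or chronic item and the functional gastrointestinal item could catch some lactose-intolerant infants, but only some. So 10.1 describes an exclusion that the lists do not contain.

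**3. Do the exit rules close the gap?** Besides ineligibility, 5.3 provides for exit when the formula must be stopped because of an adverse event or disease progression. An infant who must stop formula is therefore covered whichever eligibility passage governs. These reasons act only after enrolment, though, and do not supply the screening step that 10.1 reports.

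**The case against.** The strongest reply is that Section 4 is loose overview text in translation, while 10.2 is the section on managing adverse events and is complete on its own. The sentence before the Section 4 definition speaks of event incidence, with eczema as the example, and sets no limit by relatedness. Visits 2 to 4 and 9.6 add no limit either. A site that works from 10.2 will record everything. All of this stands, and it is why the consequence is a risk only. It does not remove the conflict, because Section 4 offers its sentence as the trial's definition and nothing subordinates it to 10.2.

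On lactose, the sentence in 10.1 is garbled: as written, its stated purpose is to increase hazards, the reverse of what must be meant. That lowers confidence in its exact content. The assertion that lactose-intolerant infants were excluded at screening is still plain.

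Three stronger readings are tempting and are not supported:

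- A reader might infer that events have been or will be under-recorded. The protocol holds nothing from which a count could be derived.
- A reader might infer that abnormal results from the planned assays are not adverse events under Section 4. Its bracket says what is included; it does not say that planned results are excluded.
- A reader might infer that the breastfed infants drop out of the safety comparison, since "The Safety Analysis Set includes all subjects who participated and received test samples with records of safety indicators" and they are assigned no study powder. Section 9.6 ties its tables to no analysis set, 10.2 also covers events over the course of the study, and the visit lists have no group limit. How a reference group without study powder is tabulated is commonly settled in a statistical analysis plan, which is not at hand here.

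**Conclusion.** Two conflicts stand in the current text. First, Section 4 makes relatedness part of the definition of an adverse event, at least for disease, and adds *unexpected*, at least for signs; 10.2 requires neither and orders full recording. Second, 10.1 reports a lactose-intolerance exclusion that appears in 0 of 9 criteria in 5.2 and 0 of 9 in the synopsis.

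Confidence is high that the passages conflict. It is lower on the exact intent of the garbled sentence in 10.1. The size in events or infants is unknown and no estimate is offered. The practical risk assumes that at least some staff work from Section 4 for recording and from 5.2 or the synopsis for screening, which the protocol permits. These are statements wrong as written, not details left to a later document, and they are cheap to correct.

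**What to change.** 1. In Section 4, delete the definition and refer to 10.2. State that relatedness is assessed after the event is recorded, as the record content in 10.2 already provides.
2. Reconcile 10.1 with 5.2 and the synopsis so that the stated safeguard and the eligibility lists agree, and repair the garbled sentence in 10.1. Which version stands is for the sponsor and investigators to decide.

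The cost is wording in Sections 4 and 10.1 and, depending on that decision, in 5.2 and the synopsis, plus the ethics committee notification that 11.3 requires for any change. Recording effort does not rise above what 10.2 already demands.
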